6.1 Staff Training

Study exams will be carried out by clinical officers and nurses who have undergone training in HPV testing, speculum exam, VIA, specimen collection, colposcopy, and biopsy. The training will be based on the International Agency for Research on Cancer (IARC), Kenya Ministry of Health (MOH) and WHO curricula and will contain didactic lectures, discussions, review of cervical photographs, and hands-on experience.^{33,8,34,35}

Several providers at FACES have already undergone training for cervical cancer screening and treatment based on cryotherapy and thermocoagulation. Additional, specific training and demonstration regarding the use of the Liger thermocoagulator will be performed by the Principal Investigator, a U.S trained Gynecologist, using instructional material, including demonstration videos, from the manufacturer. All providers will be observed performing several treatment cases to ensure competency. All study staff will undergo training in Good Clinical Practices, informed consent, participant confidentiality, and study-specific procedures.

After satisfactory completion of training, including an examination and proctored procedures, staff will receive certification. Periodic training and assessment sessions will be done throughout the study. Lab technicians will be oriented in the proper handling, storage, and transport of laboratory specimens.

6.2 Secure Data Storage and Study Files

The study will be conducted within existing clinic settings at the FACES clinics in Nyanza Province. Participant data will be collected from the participant's electronic and paper records into study-specific forms. Study-specific forms will be stored in locked file cabinets within the clinic. Data from study-specific forms will be entered into a web-based, secure data storage

platform (ODK or RedCap), with labeling by unique study ID only. A file correlating study ID and medical file number will be kept in a separate password-protected excel computer file and accessible only to the core research team. Additionally, all study computers are password protected and kept in locked offices within the clinics.

The PI is responsible for ensuring the accurate capture of study data. The information collected on study-specific forms shall be identical to that appearing in original source documents. Source documents will be found in the participant's medical records maintained by study personnel. All source documentation should be kept in separate research files for each participant. All source documentation and CTMS data will be available for review/monitoring by the UCSF DSMC and regulatory agencies.

7 Statistical Analysis Plans

Statistical analysis for all study objectives will be carried out using STATA and SPSS software.

7.1 Primary Objective

To evaluate the efficacy of thermal coagulation for the treatment of HIV-positive, HPV-positive women by assessing rates of HPV persistence and CIN2/3 at 12 months after treatment

Four hundred HIV-positive women with positive HPV testing will undergo colposcopy-directed biopsy for disease ascertainment prior to same-day treatment with thermal coagulation. At 12-months after treatment, all participants will undergo repeat HPV testing for persistence, and those who are HPV-positive will undergo repeat colposcopy, and biopsy as indicated for abnormal results, or random biopsy for 25% of those with normal colposcopy. We will define cure as a normal biopsy result or normal colposcopy among those who do not receive a biopsy.

Statistical Analysis: We will report the proportion of women with no evidence of cervical dysplasia at 12-months (primary outcome) follow-up, including 95% confidence intervals. We will extrapolate the rate of disease among those with normal colposcopy based on the rate of disease among the 25% in this group who will receive biopsy, and this will be incorporated in calculating persistence. We will perform a logistic regression to examine predictors of treatment success, using clinical and demographic variables as predictor variables. We will also report the rate of persistence of HPV at follow-up and compare with rates reported in the literature in this same population. We will compare efficacy rates for clearance of CIN2/3 to historical results following cryotherapy treatment in similar settings. A one-sample exact test will be used to compare the obtained efficacy proportion to that of historical controls.

We will leverage the robust infrastructure of the FACES in which patients are seen every one-to three months, and there is an established patient tracing system (including home visits) to reduce loss-to-follow-up. With a loss-to-follow-up rate of 10%, we will still be powered to answer this objective. Prior studies at this clinic have been able to achieve > 90% follow-up rate.³⁶ While limited by the lack of randomization to cryotherapy versus thermocoagulation, this study will provide pilot results that may enable a future randomized study evaluation of these two treatment methods.

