2.2 Primary Objective

To evaluate the efficacy of thermal coagulation for the treatment of HIV-positive, HPV-positive women by assessing rates of HPV persistence and CIN2/3 rate at 12 months after treatment

- Endpoints:
 - Proportion of women with no evidence of cervical dysplasia at 12-month follow-up based on colposcopy and biopsy.
 - Proportion of women with persistent HPV at 12-month follow-up

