3.1 Characteristics

We will prospectively enroll four hundred HIV-positive women to undergo cervical cancer screening at FACES-supported MOH clinics in Kisumu County. After informed consent, clinical and demographic information will be collected, and participants will undergo cervical cancer screening using HPV testing. Women who previously screened positive for HPV (within the last 3 months) but have not undergone treatment will also be eligible for recruitment. Women with a positive HPV test will be evaluated for treatment with thermal coagulation, per WHO standards of ablative treatment. Per the WHO and Kenya Ministry of Health guidelines, women who will be candidates for thermal coagulation if the squamocolumnar junction is fully visualized, the cervical lesion covers less than 75% of the cervix, and there is no endocervical component or suspicion of cancer.⁸ Women who are not candidates for ablation will be referred to nearby a referral facility. All participants with a positive HPV test will undergo directed biopsy just prior to treatment for disease ascertainment but proceed to have same-day treatment, according to the WHO guidelines for screen & treat.

At 12-months after treatment, all participants treated at baseline will undergo repeat colposcopy, directed biopsy for those with cervical abnormalities or those with CIN2/3 at baseline, as well as provider collected HPV testing for persistence. Twenty-five percent of women with normal colposcopy will have a random biopsy at 6 or 12-O'Clock to confirm the absence of disease. Pain will be assessed immediately following treatment using a visual analog scale (VAS). The presence and severity of AEs will be assessed 4-6 weeks following treatment via a phone call, or in person visit, if warranted. Healthcare providers offering thermal ablation for the treatment of precancerous lesions will be surveyed at 4-6 week follow-up to evaluate provider acceptability and satisfaction with this treatment method.

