3.5 Risks and Benefits

3.5.1 Potential Risks

We anticipate that the potential risks to participants in the study will be minimal. Study subjects may feel discomfort or embarrassment during the pelvic exam. There may be minimal discomfort during self-collection of HPV specimens. Participants may be at risk for psychological or emotional discomfort at different stages of the study if they have a diagnosis of CIN2/3 and learn about the potential risk of cervical cancer. Participants may risk some discomfort and mild spotting after the colposcopy and biopsy. We anticipate that this will be minimal, as exams will be performed by trained clinicians, and thermal coagulation would ablate the biopsied area with the tissue desiccation, hence stopping any bleeding. Other mechanisms to achieve hemostasis at bleeding sites including use of Silver Nitrate sticks will be available to study clinicians. Women who are not eligible for thermocoagulation due to large lesions will be referred to a nearby tertiary facility for further care, per clinic protocol. Following treatment for abnormal screening, women will have vaginal discharge for a few days for which they will be provided anticipatory guidance. During the 12-month follow-up visit, all treated women will have repeat screening with colposcopy and biopsy as needed, as well as repeat HPV-testing with provider collection. Twenty-five percent of women who have normal colposcopy results will have a random biopsy for ascertainment of cure after treatment. This may not have been performed in a routine clinical visit and may be associated with slight discomfort, but the risk to the patient will

be minimized by adequate training of clinicians, and anticipatory guidance provided to the patient. We believe that the benefit of reducing verification bias in performing these biopsies will strengthen the study results and prove a strong case for implementing this treatment method on a large scale.

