5.7.2 Provider Acceptability Evaluation

At 4-6 week follow up, providers will be surveyed using a Provider Acceptability survey, modified from the System Usability Scale to evaluate provider acceptability and satisfaction with the use of thermal coagulation for treatment of precancerous lesions.³²

5.8 12 Month Follow-up Exam

At approximately 12-months after treatment, all participants treated at baseline will undergo repeat colposcopy, biopsy for those with CIN2/3 at baseline or those with suspicious lesions on colposcopy, as well as provider collected HPV-collection for persistence. Twenty-five percent of women with normal colposcopy will have a random biopsy at 6 or 12-O'Clock for ascertainment and avoidance of verification bias.

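### Section 7.1 limits 12-month colposcopy to HPV-positive women and omits the biopsy after baseline CIN2/3, against 3.1 and 5.8 (and 3.5.1 on colposcopy); if 7.1 is followed, HPV-negative women have no defined primary outcome

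*Combined protocol and SAP*

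**What the plan says.** Three sections describe the 12-month visit in similar terms. Section 3.1: "all participants treated at baseline will undergo repeat colposcopy, directed biopsy for those with cervical abnormalities or those with CIN2/3 at baseline". Section 5.8: "all participants treated at baseline will undergo repeat colposcopy, biopsy for those with CIN2/3 at baseline or those with suspicious lesions on colposcopy". Section 3.5.1 agrees on colposcopy but is less specific on biopsy: "all treated women will have repeat screening with colposcopy and biopsy as needed, as well as repeat HPV-testing with provider collection". All three add a random biopsy in a quarter of women whose colposcopy is normal.

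Section 7.1, the analysis plan for the primary objective, differs. Everyone has the repeat HPV test, but only "those who are HPV-positive will undergo repeat colposcopy, and biopsy as indicated for abnormal results", with the random biopsy in 25% of normal colposcopies. Baseline CIN2/3 is not a reason for biopsy there.

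The endpoint in 2.2 is "Proportion of women with no evidence of cervical dysplasia at 12-month follow-up based on colposcopy and biopsy", with no condition on HPV status. Section 7.1 then adds three rules:

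- Cure: "We will define cure as a normal biopsy result or normal colposcopy among those who do not receive a biopsy".
- Unbiopsied women: "We will extrapolate the rate of disease among those with normal colposcopy based on the rate of disease among the 25% in this group".
- Comparison with cryotherapy: "A one-sample exact test will be used to compare the obtained efficacy proportion to that of historical controls".

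Section 3.3 places the non-inferiority comparison in women with CIN2/3: 140 planned, 120 after 14% loss, a reference of 77.2%, a margin of 10 points and one-sided 0.025.

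**The concern.** The section that defines the primary analysis describes a different follow-up from the sections that define the visit. Under 7.1, a woman who is HPV-negative at 12 months has neither colposcopy nor biopsy, yet cure is defined only through those two tests. The plan does not say whether she counts as cured, missing or excluded. The extrapolation cannot reach her, because it applies only to women with a normal colposcopy.

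Under 7.1, a woman with baseline CIN2/3 who is HPV-positive with a normal colposcopy has only a one-in-four chance of biopsy. The number cleared in the non-inferiority group would then be partly an extrapolated quantity, which an exact binomial test does not describe.

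At stake is the result of the non-inferiority test, which could pass or fail on a rule that nobody has written down. Tests left out at the 12-month visit may not be recoverable afterwards.

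**Working it through.** **1. The texts side by side.**

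| Section | Colposcopy at 12 months | Biopsy because of baseline CIN2/3 |
|---|---|---|
| 3.1 | every treated woman | yes |
| 3.5.1 | every treated woman | not mentioned |
| 5.8 | every treated woman | yes |
| 7.1 | HPV-positive women only | not listed |

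In 7.1, HPV-positive must mean the 12-month result. The phrase follows the repeat test in the same sentence, and all treated women were HPV-positive at baseline. The group from which the 25% is drawn also changes: normal colposcopies among all treated women in 3.1 and 5.8, but only among HPV-positive women in 7.1. The contradiction needs no calculation.

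**2. Reference behaviour of the exact test.** Boundary: 0.772 - 0.10 = 0.672. The smallest passing count with one-sided size at most 0.025 is:

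- n=140: 106 cures; size 1.8%, power 70.3% at a true rate of 77.2% and 99.9% at 85%.
- n=120: 92 cures; size 1.5%, power 60.5% and 99.4%.

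These apply if every returning woman with baseline CIN2/3 has histology and biopsy finds all disease.

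**3. Illustration if 7.1 is followed.** The documents give no test accuracies and no expected 12-month HPV-positive share. Assumed: HPV sensitivity for residual disease S = 0.85-0.95; colposcopy sensitivity and specificity 0.6-0.8; independent tests; biopsy finds all disease; share of disease-free women still HPV-positive h = 30-80%; extrapolation within the CIN2/3 group; cure count rounded down.

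*HPV-negative women counted as cured, true clearance 67.2%.* Apparent cure = 1 - 0.328 × S, which is 1 - 0.328 × 0.95 = 0.688 to 1 - 0.328 × 0.85 = 0.721. From this shift alone, the binomial probability of at least 106 of 140 is 4.6% to 19.8%. Simulating the extrapolation from the 25% sample as well gives a pass rate of about 8-28% (n=120: 7-25%), against 1.8% (1.5%). In the central case (colposcopy 0.7 and 0.7, S = 0.9, h = 40%) the pass rate is about 17%, and about 9.7 of 38.7 normal colposcopies are biopsied, so each biopsied woman stands for about four.

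*HPV-negative women excluded, true clearance 77.2%.* Apparent cure = 0.772h / (0.772h + 0.228S). For h = 30-50% this is 0.517-0.666, below the boundary. The pass rate is then at most about 7%, against 70% with everyone biopsied. For h = 60-80% apparent cure is 0.681-0.761 and the pass rate 7-50%. At a true clearance of 85% (a rate reported in section 1.3), the pass rate is 2-44% for h = 30-50% and 56-95% for h = 60-80%, against 99.9%. All are for n=140.

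**4. Whole-cohort proportion under 3.1 and 5.8 (separate point).** Assumed counts: 400 × 0.86 = 344 women; 120 with baseline CIN2/3, all biopsied; 344 - 120 = 224 others, of whom 156 have a normal colposcopy and 39 of those are biopsied; hidden disease p = 2-10% among these normals.

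- Counting unbiopsied normals as cured, minus the extrapolated estimate: 0.75 × 156 × p / 344 = 0.7 to 3.4 percentage points.
- With F the diseased proportion, the variance including the sampling is F(1-F)/344 + (156/344)² × (1/39 - 1/156) × p(1-p). With residual disease of 22.8-32.8% in the CIN2/3 group and 20-80% of the other 68 colposcopies diseased, the standard error is 1.06 to 1.38 times the binomial one.

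**The case against.** The best defence is that 7.1 only recaps the visit, loosely, while the design section and the procedure section agree with each other and with 3.5.1. If staff follow 5.8, HPV-negative women who return have a colposcopy, the cure definition classifies them, and every returning woman with baseline CIN2/3 has histology. This stands in part: the harm arises only if 7.1 prevails over three agreeing sections. It does not remove the problem, because the documents give no order of precedence and 7.1 is the section an analyst will use.

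A reader might infer several stronger things that the documents do not support:

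- **That the trial has no defined primary outcome.** This holds only for HPV-negative women, and only under 7.1's schedule.
- **That the exact test is unsuitable whatever is done.** Under 3.1 and 5.8 it applies in the CIN2/3 group.
- **That the plan intends to drop HPV-negative women.** Nothing says so, and 2.2 sets no HPV condition. Exclusion is one of several ways to fill a gap.
- **That the simulated rates measure the damage.** Apart from the critical values and the size and power of the exact test, the figures rest on assumed inputs. Section 1.2 says that HIV increases HPV persistence but gives no rate, so it does not support an HPV-positive share of 60-80%.

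It is also fair that the whole-cohort issue is distinct from the schedule conflict and smaller. No test is attached to that proportion, and the top of the standard-error range needs 10% hidden disease together with only 20% of abnormal colposcopies diseased. The cure definition and the extrapolation can be read as a rule for each woman plus a correction for the group, but 7.1 does not say so.

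**Conclusion.** The contradiction is established from the text: 7.1 conflicts with 3.1, 3.5.1 and 5.8 on who has colposcopy at 12 months, and with 3.1 and 5.8 on biopsy after baseline CIN2/3. Followed as written, 7.1 leaves HPV-negative women unclassifiable under its own cure definition and under 2.2, so this is an error in the plan rather than missing detail. It must be fixed, because it concerns the primary outcome and the group in which non-inferiority is tested.

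The consequence is conditional. Under 7.1's schedule the bias can go either way: a pass rate at the boundary of about 8-28% instead of 1.8% if HPV-negative women count as cured, and a lower chance of passing with acceptable clearance if they are excluded. These figures show direction and possible scale under assumed inputs and are not estimates for this trial. Under 3.1 and 5.8 neither effect arises in the CIN2/3 group. What remains then is the whole-cohort proportion: 0.7 to 3.4 points between the two rules in 7.1, and a binomial interval that is somewhat too narrow, on assumed counts.

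**What to change.** 1. Reconcile 7.1 with 3.1, 3.5.1 and 5.8 so that one 12-month colposcopy and biopsy schedule stands throughout.
2. State in 7.1 the outcome status of any woman who has neither colposcopy nor biopsy at 12 months.
3. If the sections are reconciled to the schedule in 3.1 and 5.8, base the exact non-inferiority test on 12-month histology in women with baseline CIN2/3.
4. Separately, for the whole-cohort proportion, use the extrapolation only and do not also count unbiopsied normal colposcopies as cured in that estimate. Because 3.1 and 5.8 biopsy all women with baseline CIN2/3, extrapolate separately for women without it. This refines the pooled rule in 7.1, which covers all normal colposcopies, and is not equivalent to it. Use a two-phase or bootstrap confidence interval that includes the 25% sampling.

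The cost is wording in 7.1 and one interval method, with no procedure beyond those already in 3.1 and 5.8. The downside is a slightly wider interval and possibly a lower reported cure rate.

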3.3 Sample Size and Power Calculation

The study sample size is calculated based on the primary objective.

We seek to enroll 400 participants in order to obtain sufficient numbers of women who have CIN2/3, our outcome of interest. Based on prior studies in this population, we anticipate approximately 35% of HPV-positive women (N ~ 140) will have biopsy-proven CIN2/3.²⁴ The study design is a non-inferiority trial using results from the only study using standard cryotherapy in a similar population¹⁹ to establish the non-inferiority boundary. We

will compare the efficacy rate in our study using thermocoagulation to the non-inferiority boundary established using the efficacy rate and lower 95% confidence bound from this cryotherapy treatment publication from a similar population.¹⁹

The efficacy results of cryotherapy in the De Vuyst paper were 77.2% (95% CI: 66.4-85.9%).¹⁹ Using 77.2% with a non-inferiority margin of 10% which is at the limit of the confidence bound and is closest to the null effect.²⁴ Using this margin, the new treatment method is hypothesized to be at least as good as cryotherapy. Based on this non-inferiority margin, a sample size of 140 women with CIN2/3 achieves 90% power in using a one-sided test with a significance level of 0.025. Based on this sample size, power of 90%, and significance of 0.025, the minimal detectable effect size (the actual difference between cryotherapy and thermocoagulation) is 0.0102.

We will leverage the robust HIV-care infrastructure at FACES in which patients are seen at every one to three months, and the presence of an established patient tracing system (including home visits) to reduce loss-to-follow-up. Assuming a 14% loss to follow-up, which would result in a sample size of 120, we are still be powered for our non-inferiority margin of 10% with a minimal detectable effect size of 0.0184, with 80% power and an alpha of 0.025. Sample size and non-inferiority calculations used NCSS PASS software and G-Power software.

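### The primary objective and cryotherapy comparison are worded in terms of CIN2/3, but the endpoint and cure rule require no dysplasia, so CIN1 at 12 months has no single classification and may not match the 77.2% benchmark.

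*Combined protocol and SAP*

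**What the plan says.** Two histology thresholds appear under one primary objective.

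**CIN2/3.** Section 2.2 sets out to evaluate efficacy by "assessing rates of HPV persistence and CIN2/3 rate at 12 months after treatment"; the synopsis and 7.1 word the objective in nearly the same way. For the external comparison, 7.1 says: "We will compare efficacy rates for clearance of CIN2/3 to historical results following cryotherapy treatment in similar settings".

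**Any dysplasia.** The first endpoint listed under that objective in 2.2 is "Proportion of women with no evidence of cervical dysplasia at 12-month follow-up based on colposcopy and biopsy". The analysis text in 7.1 labels the same quantity as primary: "We will report the proportion of women with no evidence of cervical dysplasia at 12-months (primary outcome) follow-up". The cure rule in 7.1 is: "We will define cure as a normal biopsy result or normal colposcopy among those who do not receive a biopsy".

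The benchmark is in 3.3: cryotherapy efficacy of 77.2% (95% CI 66.4 to 85.9%) from one publication, a 10-point margin, 140 women with CIN2/3 and a one-sided 0.025 test. Section 7.1 names a one-sample exact test. No section says which histology result counted as success in the 77.2%, and none mentions CIN1 at 12 months by name.

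**The concern.** Take a woman with CIN2/3 at baseline and CIN1 at 12 months. Her biopsy is not normal, so 7.1 does not count her as cured. She is not a case in the 12-month CIN2/3 rate that the objective asks for and, on the ordinary meaning of the words, she has cleared CIN2/3 for the comparison.

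Such women can be detected. Sections 3.1 and 5.8 plan a 12-month biopsy for everyone with CIN2/3 at baseline, and section 1.2 describes raised HPV incidence and persistence in this population. The documents give no CIN1 frequency.

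The study has no concurrent cryotherapy arm. In a randomised comparison both arms would be graded by the same rule. Here the observed proportion is set against a fixed external number, so a difference between the study's threshold and the benchmark's passes straight into the result as bias, on a margin of only 10 points.

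**Working it through.** **Inputs from the documents**
- Benchmark 77.2%, margin 10 points (3.3): boundary p0 = 0.772 − 0.10 = 0.672.
- n = 400 × 0.35 = 140 women with CIN2/3 (3.3). With 14% loss, 140 × 0.86 = 120.4, or 120 as stated.
- One-sided alpha 0.025 (3.3); one-sample exact test (7.1).

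**Assumption, not in the documents**
- A share x of the women with baseline CIN2/3 have CIN1 and nothing worse at 12 months. Range shown: 0 to 10%.

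**The plan's own figure.** Section 3.3 states 90% power for n = 140 with an actual difference of 0.0102. The exact test does not reproduce this: power is 70.3% at a true rate of 77.2% and 79.6% at 77.2% + 1.02 = 78.22%. That is a separate matter. The calculations below use the exact test.

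**Decision rule.** The cut-off k is the smallest number with P(X ≥ k | n, 0.672) ≤ 0.025.
- n = 140: k = 106, attained size 0.018.
- n = 120: k = 92, attained size 0.015.

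**Case A: the benchmark counted CIN1 as cleared, the study counts it as failure.** True CIN2/3 clearance is 77.2%, so the no-dysplasia rate is 0.772 − x. The chance of success is P(X ≥ k | n, 0.772 − x).

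| x | CIN1 cases of 140 | No-dysplasia rate | n = 140 | n = 120 |
|---|---|---|---|---|
| 0 | 0 | 77.2% | 70.3% | 60.5% |
| 2% | about 3 | 75.2% | 48.9% | 40.1% |
| 5% | 7 | 72.2% | 20.3% | 16.1% |
| 10% | 14 | 67.2% | 1.8% | 1.5% |

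With CIN1 counted as cleared, the chance stays at 70.3% (n = 140) or 60.5% (n = 120) whatever x is.

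**Case B: the benchmark counted CIN1 as failure, the study counts it as cleared.** The true no-dysplasia rate is at the boundary, 67.2%, so non-inferiority should rarely be declared. The study observes 0.672 + x.

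| x | Rate the study sees | False non-inferiority, n = 140 | n = 120 |
|---|---|---|---|
| 0 | 67.2% | 1.8% | 1.5% |
| 2% | 69.2% | 5.5% | 4.5% |
| 5% | 72.2% | 20.3% | 16.1% |
| 10% | 77.2% | 70.3% | 60.5% |

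**Case C: the thresholds match.** This bias is zero, whichever threshold it is.

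**One data set, two answers.** If 108 of 140 women clear CIN2/3, then 108 ≥ 106 and the test passes. If three of those 108 have CIN1, 108 − 3 = 105 have no dysplasia and the test fails.

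**The case against.** The strongest reply is that the plan already has one operative definition. Section 7.1 attaches the primary-outcome label to the no-dysplasia proportion, the cure rule fits it, and so does the first endpoint in 2.2. A normal-biopsy rule makes CIN1 a non-cure by implication. Clearance of CIN2/3 can then be read as cure, so defined, among women who had CIN2/3 at baseline. That reading suits the hypothesis in 2.1 and the 140-woman denominator, and it would bring the comparison into line with the cure rule. Section 7.1 also describes the results as pilot results.

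Much of this stands, and it rules out several stronger readings that a reader might infer:

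- That the outcome is left wholly open until the data are seen. It is not, because 7.1 names a primary outcome.
- That 3.3 sets a CIN2/3 threshold at 12 months with "women who have CIN2/3, our outcome of interest". In context that phrase explains how many women with CIN2/3 must be enrolled. It describes baseline disease and the denominator.
- That progression to cancer would escape the analysis. Under the normal-biopsy rule, cancer shown on biopsy is already a failure. Only the CIN2/3 wording omits it.
- That the bias is known in direction or size. It depends on an assumed CIN1 share and on a benchmark definition that the documents do not give.
- That absence of CIN2 or worse ought to be the primary outcome. The documents do not support choosing it over no dysplasia. If the benchmark required no dysplasia, that choice would create Case B.

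The reply does not remove the point. The favourable reading of the comparison is nowhere stated, the objective's CIN2/3 rate still disagrees with its own endpoint, and nothing links the study's threshold to the one behind the 77.2%. Pilot status does not help either, since 3.3 frames the study as a non-inferiority trial with a stated boundary.

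**Conclusion.** The concern holds as an inconsistency in the current text together with an unverified match to the benchmark. The inconsistency needs no calculation. Its effect can decide the non-inferiority conclusion: in the illustration with 140 women, an assumed 5% with CIN1 (7 women) moves the chance of success from 70% to 20% under one mismatch, and false non-inferiority from 2% to 20% under the other. These figures rest on the exact test at one-sided 0.025, the assumed CIN1 shares, and a true rate of 77.2% (Case A) or exactly at the boundary (Case B). They show sensitivity and do not predict what will happen. Confidence is high for the wording conflict; the actual bias cannot be established from the documents and may be zero.

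**What to change.** 1. Before analysis, establish from the cited cryotherapy publication which histology result counted as success in the 77.2%, and record it in 3.3.
2. In 2.2 and 7.1, state that the non-inferiority comparison among women with baseline CIN2/3 uses that same threshold. Say explicitly how CIN1 at 12 months is classified, and that invasive cancer is always a failure.
3. Align the objective and endpoint wording in the synopsis, 2.2 and 7.1 to one primary threshold.
4. Report the other threshold (no dysplasia, or no CIN2 or worse) as a prespecified secondary or sensitivity result.

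The cost is a check of one source and a few sentences. Histology from the planned biopsies can be analysed at either threshold, so no extra procedure is needed. The downside is that one of the two definitions is no longer the headline.
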